## **7.2 Statistical analysis**

**Objectives 1 and 2** (Speech in Noise OLSA): The SRT data will be analyzed using a one-tailed paired t-test.

**Objectives 3 and 4** (Speech in Quiet Freiburger): Similarly to the OLSA Test the % correct data will be analyzed using a one-tailed paired t-test.

**Objective 5** (NAL-NL2 Targets): No statistical analysis will be performed, only descriptive statistics will be used.

**Objectives 6-7** (Questionnaires – SSQ17, IOI-HA)

Subjective rating data from real-life questionnaires will be analyzed using one-tailed paired t-tests, comparing ratings of study HA and own HA with a significance level of 0.05 to determine significance.

In addition, descriptive statistics of the SSQ 17 scores and IOI-HA scores will be reported by Hearing Aid (study or own) for each subscale and put into perspective of published data (von Gahlenz et al, 2018; Cox et al, 2013).

**Objective 8** (Questionnaire – Satisfaction)

One-sided test of proportions will be done to analyze whether the proportion of satisfied hearing aid users is significantly lower with study hearing aids than reported in the literature (MarkeTrak 10, EuroTrak). A significant effect indicates that the study hearing aids are inferior, otherwise they are non-inferior.

In addition, subjective rating data from satisfaction questionnaire will be analyzed using one-tailed paired t-tests, comparing ratings of study HA and own HA with a significance level of 0.05.

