## **4.2 Hypotheses**

### **4.2.1 Primary objectives**

The **primary objectives 1 and 2** will be addressed by measuring a speech reception threshold (SRT) for each hearing aid, using an adaptive speech-in-noise test, OLSA. The SRT corresponds to the signal-to-noise ratio (SNR) where 80% of the words presented are correctly repeated by the test subject. Thus, a lower SRT value indicates better performance.

The difference between the study HAs and the subjects' own HAs or no HAs will be assessed as the mean SRT difference. The expectation is that the study HAs give an advantage over not wearing HAs so the first hypothesis is:

**$H_0$  (Objective 1)** SRT(study HA) is not significantly different from SRT without HAs

**$H_1$ (Objective 1)** SRT(study HA) is significantly better than SRT without HAs

A mean difference in SRT of 1 dB measured with the Oldenburg sentence test (Wagener et al, 1999a-c), can be assumed as a typical difference in speech intelligibility to show a clinically meaningful improvement (Kollmeier et al, 2011).

In addition, the expectation is that the study HAs are not inferior to the subjects' own HAs:

**$H_0$  (Objective 2)** SRT(study HA) is significantly worse than SRT(own HAs).

**$H_1$ (Objective 2)** There is no difference between SRT(study HA) and SRT(own HAs)

A significant difference means that the study HAs are inferior to own HAs, otherwise they are non-inferior. .

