For the **secondary objective 8**, to evaluate satisfaction, subjects are asked to rate their satisfaction with the hearing aids regarding several aspects including sound, conversations and overall satisfaction after having worn the hearing aids 10-14 days in real-life. In Marke-Trak10 survey (Picou, 2020), respondents rated their satisfaction on a 7-point scale, where 1 indicates very dissatisfied, 4 indicates neutral, and 7 indicates very satisfied. Respondents who indicated scores of 5, 6, or 7 were considered to be satisfied and satisfaction was reported as % satisfied of the study sample. In a similar manner the percentage of satisfied subjects will be calculated for the study HAs and compared to published values of (MarkeTrak10 (Picou, 2020) and EuroTrak German (2022 ), EuroTrak France (2022), EuroTrak Spain (2023) ). For each question we will test whether the proportion of satisfied subjects is significantly lower with study HAs compared to the published values (MarkeTrak/EuroTrak), if they are, that

indicates the study hearing aids are inferior the hearing aids reported on in the MarkeTrak/EuroTrak Reports. Otherwise, they are non-inferior.

In addition, mean ratings will be calculated across the participants and will be compared for the study HAs and own HAs and for each question we will test whether the ratings are significantly worse with study HAs compared to own HAs, if they are, that indicates the study hearing aids are inferior to own HAs. Otherwise, they are non-inferior.

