## 7. Statistical design and analysis

### 7.1 Sample size estimation

The sample size is determined by considering the primary objective 1 and the related hypothesis expecting a mean difference in SRT between the study HA and no HA of at least 1 dB.

Speech intelligibility in noise is usually determined as a speech intelligibility threshold in dB SNR, so a difference between dependent mean values is analyzed. The data for these data are expected to be normally distributed, so a t-test is used to estimate the number of cases.

A mean difference in SRT of 1 dB measured with the Oldenburg sentence test (Wagener et al, 1999a-c), can be assumed as a typical difference in speech intelligibility to show a clinically meaningful improvement (Kollmeier et al, 2011).

The interindividual standard deviation in hearing-impaired test subjects for this method with the stationary noise associated with the test is 1.3 dB (Wagener & Brand, 2005). Assuming that dependent mean values for two comparative measurements show a high correlation (0.8), this results in an average effect size for the method (effect size  $dz$ ) of 0.77 and, with an  $\alpha$  value of 0.05 and a  $\beta$  value of 0.2 (power = 0.8), a number of cases of  $n = 16$ , calculated using the G\*Power (3.1.9.7) program of the University of Düsseldorf (Faul et al., 2007),

With an added 25% dropout risk this suggests that recruiting 20 subjects will be appropriate with respect to addressing the primary objectives and testing the related hypothesis.  $N = 20$  subjects will provide a statistical power of 0.9 when the other parameters are kept constant.

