## **12. Publication policy**

The data collected in the study is primarily aimed for WSA regular PMCF report but may be published in white papers and/or trade journal papers. All data are presented in a fully anonymized form. Only descriptive statistics are presented, like mean values, standard deviations and counts of participants.

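### Objective 8 declares the study aids non-inferior on satisfaction whenever a one-sided test in about 20 subjects is not significant, with no margin

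*Combined protocol and SAP*

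**What the plan says.** Section 4.2.2 has subjects rate their satisfaction "regarding several aspects including sound, conversations and overall satisfaction" on a 7-point scale, with scores of 5 to 7 counted as satisfied. On the survey comparison it states: "For each question we will test whether the proportion of satisfied subjects is significantly lower with study HAs compared to the published values". A significantly lower proportion "indicates the study hearing aids are inferior the hearing aids reported on in the MarkeTrak/EuroTrak Reports. Otherwise, they are non-inferior". Section 7.2 specifies a one-sided test of proportions and repeats the reading: "A significant effect indicates that the study hearing aids are inferior, otherwise they are non-inferior".

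The paired comparison of mean satisfaction ratings, study aids against own aids, is read in the same way in Section 4.2.2: "if they are, that indicates the study hearing aids are inferior to own HAs. Otherwise, they are non-inferior". Section 7.2 sets its significance level at 0.05. It gives no level for the test of proportions.

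On size, Section 7.1 says: "The sample size is determined by considering the primary objective 1 and the related hypothesis". It arrives at 20 recruited subjects. No published satisfaction rate, satisfaction margin, or power for Objective 8 appears.

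The rule is not confined to Objective 8. Section 4.2.1 applies it to Objective 2 ("A significant difference means that the study HAs are inferior to own HAs, otherwise they are non-inferior"), and Section 4.2.2 applies it to Objectives 4, 6 and 7.

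**The concern.** A test whose null hypothesis is no deficit can give evidence of a deficit. When it fails to reject, it does not show that the deficit is absent or small. Non-inferiority requires a stated margin and a confidence bound that excludes a deficit of that size. This plan has neither, so the label depends on the test not having found anything, and that becomes easier as information shrinks. With about 20 subjects, the report could call the study aids non-inferior to MarkeTrak/EuroTrak on a question while the interval for that question still contains a large shortfall. Because the test is run question by question, the label can be given separately on each one.

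**Working it through.** **The plan's own figure.** Section 7.1 gives n = 16 for power 0.8 and power 0.9 at N = 20, for Objective 1. Taking its dz = 0.77, a paired t-test at two-sided 0.05 (noncentral t) has power 0.821 at n = 16 and 0.904 at n = 20, so both figures reproduce. They concern the OLSA threshold only. Nothing comparable exists for satisfaction.

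**Inputs for the survey comparison.** From the documents: a one-sided test in the direction of lower satisfaction, one question at a time, 20 subjects. Assumed, because the documents do not say: benchmark p0 of 70%, 75%, 80%, 85% or 90%, treated as fixed; an exact or uncorrected normal one-sample test; alpha 0.05; no dropout.

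**Formula.** Let X be the number satisfied and c the largest count called inferior. For the exact test, c is the largest count with P(X ≤ c | 20, p0) ≤ 0.05. For the normal test, it is the largest count with (c/20 − p0)/√(p0(1 − p0)/20) ≤ −1.645. If the true rate is p0 − d, the chance of the non-inferior label is P(X > c | 20, p0 − d).

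| p0 | c, exact/normal | d = 10 points | d = 15 points | d = 20 points |
|---|---|---|---|---|
| 70% | 10/10 | 0.755 | 0.591 | 0.412 |
| 75% | 11/11 | 0.762 | 0.596 | 0.414 |
| 80% | 12/13 | 0.772/0.608 | 0.601/0.417 | 0.416/0.250 |
| 85% | 13/14 | 0.786/0.617 | 0.608/0.416 | 0.417/0.245 |
| 90% | 15/15 | 0.630 | 0.415 | 0.238 |

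Single entries mean that the two tests agree. The lower values at 80% and 85% come from a normal test whose actual size there is 0.087 and 0.067, above the nominal 0.05. For benchmarks of 91% to 95%, a 10-point deficit is labelled non-inferior with probability 0.550 to 0.715 (exact) or 0.358 to 0.550 (normal).

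**One result, worked through.** Suppose 14 of 20 (70%) are satisfied and p0 = 80%.
- Exact: P(X ≤ 14 | 20, 0.80) = 0.196.
- Normal: (0.70 − 0.80)/√(0.80 × 0.20/20) = −0.10/0.0894 = −1.118, p = 0.132.
- Exact 95% CI: 45.7% to 88.1%.

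Both tests give the label, although the data are compatible with a rate more than 30 points below the benchmark.

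**Fewer subjects.** With n = 16 (the Section 7.1 number before the dropout allowance), p0 = 80% and the exact test, the label is given with probability 0.825 for a 10-point deficit and 0.527 for a 20-point deficit. With 20 subjects these are 0.772 and 0.416.

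**Paired comparison.** Inputs: one-tailed paired t-test at 0.05 (Section 7.2), n = 20, differences assumed normal. With 19 degrees of freedom the critical value is 1.729, and the noncentrality is dz × √20, where dz is the true deficit in SDs of the differences.

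| dz | P(labelled non-inferior) |
|---|---|
| 0.2 | 0.783 |
| 0.3 | 0.637 |
| 0.4 | 0.468 |
| 0.5 | 0.305 |

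**The case against.** The strongest points on the other side are these.

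- **The magnitudes rest on assumptions.** This stands. The documents give no published rates, test variant, alpha for the proportion test, or satisfaction difference that would matter. The figures are therefore ranges, but the fault needs none of them: at any benchmark there is no margin and no confidence-bound criterion.
- **Power is not poor for every shortfall.** This also stands. Over benchmarks of 70% to 90%, a 20-point deficit is flagged 58% to 76% of the time (1 − 0.417 and 1 − 0.238). The weakness is greatest for deficits of around 10 points.
- **Objective 8 is secondary, and the same rule matters more for primary Objective 2.** This is true and limits the severity. Objective 8 still needs its own repair, because it compares a proportion with external rates and a margin in dB would not carry over. Section 1.4 also places non-inferior performance ratings against own aids within the overall main hypothesis.
- **Section 12 limits what is published: "Only descriptive statistics are presented, like mean values, standard deviations and counts of participants".** That governs presentation. It does not withdraw the decision rule in Sections 4.2.2 and 7.2, and Section 12 itself says the data are mainly for the sponsor's PMCF report.

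**Conclusion.** The concern holds: the decision rule for Objective 8 is wrong as written, for both the survey comparison and the paired comparison. Under the assumptions above (n = 20, one-sided 0.05, benchmarks of 70% to 90%, either test), a true deficit on one question against one benchmark is labelled non-inferior 61% to 79% of the time at 10 points, 41% to 61% at 15 points and 24% to 42% at 20 points. In the paired comparison the figure is 78% at a deficit of 0.2 SD of the differences and 47% at 0.4 SD. These are rates per question, not for the device as a whole, since the plan states no overall satisfaction verdict. The point should be corrected. It does not touch the superiority test of Objective 1.

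**What to change.** In Sections 4.2.2 and 7.2, delete the clause that turns a non-significant result into non-inferiority, for both Objective 8 comparisons. For each question, report the proportion satisfied with its exact 95% CI beside each published value, and the paired study-minus-own mean difference with its CI, without a label.

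If a claim is wanted, prespecify one benchmark and a justified margin, and claim non-inferiority only if the exact one-sided 95% lower bound exceeds benchmark minus margin. As an illustration only, take 80% and 15 points, so the bound must exceed 65%. The bound is 59.9% for 16/20 and 65.6% for 17/20, so at least 17 satisfied are needed. A device truly at 65% reaches that 4.4% of the time, and one truly at 80% reaches it 41% of the time.

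For Objective 8 this is a change of wording with no new data. Section 10 requires ethics committee approval of any amendment. The price is that, with 20 subjects, the survey comparison becomes descriptive, and a margin-based claim would usually fail even for a device that matches the benchmark in this illustration.

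The same reading should be corrected consistently for Objectives 2, 4, 6 and 7. That is a larger step, because Objective 2 is primary and Sections 1.4 and 4.1 also use non-inferiority wording that would have to be aligned.

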## **8. Deviations from clinical investigation plan**

A protocol deviation is any noncompliance with the clinical investigation plan. The noncompliance may be either on the part of the subject, the investigator, or the study site staff.

As a result of deviations, corrective actions are to be developed by the site and implemented promptly. Prior approval by the sponsor is required for changes in or deviations from the plan. It is the responsibility of the study partner to use continuous vigilance to identify and report deviations.

All deviations must be addressed and reported to the sponsor.

## **9. Device preparation/handling/storage/accountability**

### **9.1 Acquisition and accountability**

Sponsor will deliver the hearing aids to the investigation site before the first subject is enrolled in the study.

If for any reason devices need to be returned to the sponsor, investigator site will be responsible to safely send the respective devices back.

Return of all devices will be with responsibility of the investigator site to send those safely back to the sponsor site directly after the close out virtual meeting with the investigation site.

### **9.2 Product storage and stability**

Devices should be stored in their designated jewel cases or appropriate trays or boxes. Temperature for storage should be between 10 to 40 °C (50 to 104 °F). Relative humidity should be 10 to 80% and Atmospheric pressure 700 to 1060 hPa.

### **9.3 Preparation**

Randomization coding need to be done in advance by the designated investigational site staff.

### **9.4 Randomization and blinding coding**

The study design does not allow for the study to be blinded. REM Measurements will only be done with the study HAs and during Home-Trial, subjects are well aware of which HA they are wearing. For the speech tests the order of study HA, own HA and unaided will be randomized.

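### Speech-test order is randomised, but its balance is not specified and the paired t-tests ignore test position, so any practice or fatigue effect is left in the error variance (cheap improvement)

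*Combined protocol and SAP*

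**What the plan says.** The workflow table in section 6.3 places both speech tests (Freiburger in quiet, OLSA in noise) in the second lab visit, each under three conditions: unaided, study aids and own aids. No practice list is mentioned.

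On order, section 9.4 says "For the speech tests the order of study HA, own HA and unaided will be randomized", and section 9.3 adds "Randomization coding need to be done in advance by the designated investigational site staff". Neither section mentions blocks, a Latin square or balance over the six orders, and neither rules them out. Nor do they say whether one order serves both tests.

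For Objectives 1 and 2, section 7.2 says "The SRT data will be analyzed using a one-tailed paired t-test". The Freiburger scores (Objectives 3 and 4) are handled in the same way. No order or position term appears.

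Section 4.2.1 gives Objective 2 no margin: if the study aids are not significantly worse than the own aids, they are called non-inferior.

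**The concern.** Repeated speech testing in one sitting can produce learning or tiredness. Randomising the order keeps this from favouring one condition systematically. A paired t-test that ignores position, however, treats every position effect as unexplained noise: a subject tested unaided first and with the study aids third contributes a difference that contains two steps of drift.

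The stake is precision in both primary comparisons and in the Freiburger comparisons. For Objective 1, lost precision means lost power. For Objective 2, the rule in section 4.2.1 rewards a non-significant result, so extra noise works in favour of the study aids. The plan already generates the information that would remove this noise but does not use it.

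**Working it through.** **Inputs from section 7.1.** The target is described as "expecting a mean difference in SRT between the study HA and no HA of at least 1 dB". The spread is given as: "The interindividual standard deviation in hearing-impaired test subjects for this method with the stationary noise associated with the test is 1.3 dB". The correlation is introduced by "Assuming that dependent mean values for two comparative measurements show a high correlation (0.8" in parentheses. The section also gives an effect size dz of 0.77, alpha 0.05, power 0.8, n = 16, and power 0.9 at N = 20.

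**The plan's own figures.** Exact paired t-test power (noncentral t) with dz = 0.77 and two-sided alpha 0.05 is 0.792 at n = 15, 0.821 at n = 16 and 0.904 at n = 20. So n = 16 and power 0.9 reproduce, as two-sided figures. The planned test is one-tailed, which gives 0.95 at N = 20.

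**Which SD of differences.** dz = 0.77 equals 1/1.3, so it implies an SD of differences of 1.3 dB (a correlation of 0.5). The stated correlation of 0.8 gives 1.3 × √(2 × (1 − 0.8)) = 0.82 dB. The documents do not settle which applies, so both are carried through.

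**Variance added by position.** Let scores shift by d dB per test position. Over six equally likely orders, two given conditions are one position apart in four orders and two apart in two. The position difference has mean 0 and variance (2/3) × 1² + (1/3) × 2² = 2. Each paired difference therefore gains variance 2d². For example, at d = 0.5 the SD becomes √(1.69 + 0.50) = 1.48 dB.

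The documents give no value for d. The range below is an assumption. Power is one-tailed for a true 1 dB difference, with simple randomisation and the unadjusted t-test.

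| d (dB per position) | SD, from 1.3 | Power, N = 20 | Power, n = 16 | SD, from 0.82 | Power, N = 20 |
|---|---|---|---|---|---|
| 0 | 1.30 | 0.95 | 0.90 | 0.82 | >0.99 |
| 0.25 | 1.35 | 0.94 | 0.88 | 0.90 | >0.99 |
| 0.5 | 1.48 | 0.90 | 0.82 | 1.08 | 0.99 |
| 1.0 | 1.92 | 0.73 | 0.63 | 1.64 | 0.84 |

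With SD 1.3 dB and N = 20, power drops below 0.80 only when d exceeds about 0.8 dB per position. If only the first test differs from the other two, the added variance is (2/3)d², and power is 0.94 at d = 0.5 and 0.88 at d = 1.

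**Validity.** In simulations of 20,000 trials per setting at N = 20, the unadjusted t-test under simple randomisation had type I error between 0.049 and 0.052, and the mean difference was unbiased.

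**Balance without adjustment.** With near-balanced orders (SD 1.3 dB) the plain t-test becomes conservative: type I error is 0.032 at d = 0.5 and 0.009 at d = 1. Balance removes the position effect from the mean difference, but the sample SD still contains it, so the standard error is too large. Power is 0.92 and 0.78, somewhat better than under simple randomisation but short of what adjustment gives.

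**Balance with adjustment.** Regress each paired difference on two terms: the difference between the two conditions in the indicator for position 2, and the same for position 3. Test the intercept on 20 − 3 = 17 degrees of freedom. With near-balanced orders and SD 1.3 dB, type I error is about 0.05 and power about 0.95 at every d in the table. At d = 0 the mean 95% CI width is 1.21 dB against 1.20 dB unadjusted. Adjusting under simple randomisation, without balance, gives power of about 0.93 at every d simulated (0, 0.5 and 1 dB).

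**Objective 2.** If the study aids were truly 1 dB worse, the chance of a non-significant result, read as non-inferior, is one minus the power. With SD 1.3 dB, simple randomisation and no adjustment, that is 4.8% at d = 0, 10.3% at d = 0.5 and 27.5% at d = 1.

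**The case against.** The strongest reply is that randomising the order already does what is needed: the comparison is unbiased and the t-test keeps its level. That is correct, and the point here concerns precision only.

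A reader might infer more than the documents support, in four ways.

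- **That the orders are unbalanced.** The documents are silent. A list prepared in advance by site staff (section 9.3) is compatible with balance. What can be said is that balance is not specified.
- **That the study is underpowered for Objective 1.** No position effect is reported. The top of the assumed range means 2 dB of drift from first to third test, twice the difference the plan calls clinically meaningful. At 0.5 dB per position, power is still 0.90, matching the plan's stated figure. With the stated correlation of 0.8 it stays at 0.84 or above throughout.
- **That chance imbalance is a further bias.** Its effect on the estimate is already counted in the 2d² term and in the t-test's standard error.
- **That the Objective 2 problem comes from test order.** Noise favours a non-inferior finding mainly because there is no margin. A position term leaves that rule in place.

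It can also be objected that a mixed model pooling error over the three conditions assumes equal variances and gains part of its apparent advantage from extra error degrees of freedom. That stands. It does not apply to the regression above, which uses only the two conditions being compared and held type I error near 0.05 when the conditions had unequal variances.

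Finally, no figure can be given for the Freiburger tests, because the documents supply no SD on the percent scale. The mechanism is the same, but its size there is unknown.

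**Conclusion.** The point holds as a cheap improvement. The order is randomised, its balance is not specified, and the planned t-tests ignore position, so any practice or fatigue effect enlarges the error variance. How much is lost depends wholly on an effect the documents do not quantify: nothing at zero, little up to about 0.5 dB per position, and a material loss near 1 dB per position if the SD of differences is 1.3 dB. The figures assume a linear shift, normal differences and simple randomisation; if site staff already balance the list, the unadjusted test is conservative instead. The primary comparisons are neither biased nor, under simple randomisation, subject to an inflated false-positive rate.

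**What to change.** **Section 9.4.** State that subjects are allocated to the six orders in balanced blocks of six, and whether the same order is used for both tests. Twenty subjects allow near-balance only: three per order for 18, and the last two on different orders.

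**Section 7.2.** Make the primary analysis of the OLSA and Freiburger scores the within-subject difference adjusted for test position. One way is to regress each paired difference on the two position-difference terms and test the intercept one-sided. A mixed model with condition and position as fixed effects and subject as random is an alternative, provided condition-specific variances are fixed in advance and not chosen after seeing the data.

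**Do not rely on the unadjusted t-test once orders are balanced.** With a position effect its type I error falls to about 0.03 (0.5 dB) or 0.01 (1 dB). Compared with the adjusted test, that makes a non-inferior finding easier to reach under section 4.2.1.

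**Cost.** A balanced list, a sentence or two in section 7.2, two degrees of freedom, and about 0.01 dB of CI width if there is no position effect. No extra subjects, visits or measurements are needed. The missing margin for Objective 2 must be dealt with separately.
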